### Baseline Characteristics and Differences

Descriptive statistics (means and standard deviations in case of normally distributed variables or medians and interquartile ranges in case of non-normally distributed variables, and numbers and percentages in case of categorical variables) will be reported for the following baseline characteristics:

- Sociodemographic variables: age, sex, marital and relationship status, education
- Disease- and treatment related variables: medication, duration of OA, comorbidities, OA in other joint sites, previously received treatments for OA
- Physical examination: Doyle index (total score and sub scores hand and knee/hip joints), hand strength
- Other: frequency of internet use, proficiency of internet use, extraversion and neuroticism

Differences in baseline characteristics between the intervention group and control group will be examined, and between patients who completed the intervention and those who did not. For continuous outcomes, T-tests or independent samples median tests (when non-normally distributed) will be conducted. For categorical outcomes,  $\chi^2$ -tests will be conducted.

### Analyses

All main analyses will be carried out following the intention-to-treat (ITT) principles. As linear mixed models are well-suited to handle missing values, missing data from drop-outs will not be imputed. Person-mean imputation will be applied when necessary to calculate scale scores. The analyses will be conducted (1) with the inclusion of covariates (primary analysis), (2) without the inclusion of covariates (sensitivity analysis) and (3) per protocol (i.e., comparing only the patients who completed the intervention with patients in the control group as a sensitivity analysis) with and without the inclusion of covariates.

### Main Analyses

To compare changes in primary and secondary outcome variables during the study period between patients in the intervention and control groups, linear mixed models will be fitted using full maximum likelihood estimation. The models will include fixed effects of time as three dummy variables: 'short-term' for baseline vs. post-intervention, 'mid-term' for baseline vs. 6-week follow-up, and 'long-term' for baseline vs. 3-month follow-up. To indicate the effect of the intervention across time, the fixed effects of interactions between group (i.e., intervention or control group) and timepoint will be included as again three dummy variables: short-term\*group, mid-term\*group, and long-term\*group. Finally, the fixed effects of the covariates age (centered) and sex will be included. The models will include random effects of intercept and the addition of random effects of slopes will be tested with Likelihood Ratio Tests (i.e., the difference in -2LL between the alternative model and the null model using a  $\chi^2$  distribution). For each model, the variance-covariance matrix leading to the optimal model fit (i.e., the lowest Akaike's Information Criterion) will be selected using restricted maximum likelihood estimation. Values of  $p < .05$  (two-tailed) will be considered as significant.

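### On the plain reading, group-by-time tests use full maximum likelihood with no degrees-of-freedom method, so they run slightly liberal: a minor point

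*SAP*

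**What the plan says.** SAP, Main Analyses, uses two estimators. For comparing change between the groups, "linear mixed models will be fitted using full maximum likelihood estimation". For the covariance matrix, the best-fitting structure by Akaike's criterion "will be selected using restricted maximum likelihood estimation".

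The fixed part is set in advance: an intercept, three time dummies ("The models will include fixed effects of time as three dummy variables"), three interactions ("short-term\*group, mid-term\*group, and long-term\*group"), and two covariates ("the fixed effects of the covariates age (centered) and sex will be included"). That makes nine fixed effects, with no group main effect listed. A random intercept is always present, and random slopes are tested by likelihood ratio. Significance is two-sided at .05. Under Analyses, "missing data from drop-outs will not be imputed", and per-protocol runs are added.

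The section does not say which fit supplies the reported coefficients and p-values. It gives no degrees-of-freedom or small-sample method.

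**The concern.** Full ML estimates variance components as if the fixed effects were known, so it understates them, and the standard errors of the contrasts shrink with them. REML corrects for this. The plan uses REML to choose the covariance structure but, as written, not for the fit whose variances feed the tests.

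Full ML is needed to compare, by likelihood, models that differ in their fixed effects. The SAP plans no such comparison. The runs with and without covariates are sensitivity analyses, and the random-slope test and the covariance choice each keep the fixed effects the same, so both can be done under REML.

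At stake are the p-values and confidence limits for pain coping and every secondary outcome, at three follow-up times, in the intention-to-treat and per-protocol runs.

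**Working it through.** The SAP gives no sample size, standard error or power figure, so there is nothing of its own to reproduce.

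**Inputs.** From the SAP: four occasions, the nine fixed effects above, a random intercept, two-sided .05. Assumed, because not stated: total N of 50 to 200 in two equal groups, drop-out as noted, intra-class correlation 0.5 or baseline/follow-up correlation 0.6.

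**1. Standard-error ratio, complete data.** With a random intercept and a group main effect, the within-patient variance is divided by 3N under ML and by 3N − 6 under REML (three time and three interaction terms). Hence

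SE(ML)/SE(REML) = √[(3N − 6)/(3N)] = √(1 − 2/N).

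An unstructured matrix without a group main effect gives divisors N and N − 2, so the ratio is the same. A result lying exactly at p = .05 under ML then has p = 2[1 − Φ(1.96·√(1 − 2/N))] under REML (normal approximation).

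| N | ratio | shortfall | REML p when ML p = .050 |
|---|---|---|---|
| 50 | 0.980 | 2.0% | .055 |
| 60 | 0.983 | 1.7% | .054 |
| 100 | 0.990 | 1.0% | .052 |
| 200 | 0.995 | 0.5% | .051 |

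**2. The listed model, simulated** (random intercept, age and sex, 1,500 trials per setting). Without a group main effect, the interaction standard errors fall short by 2.2%, 1.1% and 0.55% at N = 50, 100 and 200. With 20% drop-out the figures are 2.4%, 1.2% and 0.6%. With a group main effect they are 2.0%, 1.0% and 0.5%, and 2.3%, 1.15% and 0.58% with drop-out. Age and sex behave differently: their standard errors fall short by about 3.4–4.2%, 1.7–2.1% and 0.85–1.0%.

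**3. Type I error, unstructured matrix, no group main effect, baseline and one follow-up, complete data.** The estimate is the baseline-adjusted group difference. Its model-based standard error is √(v·4/N), where v = RSS/N under ML and RSS/(N − 2) under REML. The exact standard error is √{RSS/(N − 3)·(4/N + D²/S)} with N − 3 degrees of freedom, where D is the observed baseline difference and S the pooled within-group baseline sum of squares. Let U = 1/[1 + N·D²/(4S)], which follows Beta((N − 2)/2, 1/2), and let c be the 97.5% t quantile on N − 2 degrees of freedom. Then

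rejection rate = E{2·P[t(N − 3) > c·√(k·U)]}, with k = (N − 3)/N for ML and (N − 3)/(N − 2) for REML.

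| N | ML | REML | exact adjustment |
|---|---|---|---|
| 60 | 5.8% | 5.4% | 5.0% |
| 100 | 5.5% | 5.2% | 5.0% |
| 200 | 5.2% | 5.1% | 5.0% |

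Simulations of the same set-up (200,000 to 400,000 trials per N) agree: ML 5.7–5.9%, 5.5% and 5.2–5.3%; REML 5.3–5.5%, 5.2–5.3% and 5.1%.

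**4. Type I error, random intercept with a group main effect, t reference on 3N degrees of freedom for ML.** ML runs at 5.5%, 5.2% and 5.1% for N = 50, 100 and 200. REML on its own 3N − 6 degrees of freedom is at 5.0%.

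**The case against.** The best defence is that this hardly matters. Full ML is a legitimate and consistent estimator, and a likelihood ratio test for random slopes is permissible under it. Switching to REML moves the error rate by roughly 0.1 to 0.5 percentage points. That stands, and it is why the point is minor.

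The text also leaves room for another reading. The structure is selected with REML for each model, so the sponsor may intend to report that fit. ML is the plainer reading, but the text does not settle it. An unstated choice between two sets of output still needs settling before analysis.

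Three stronger inferences are tempting, and the document does not support them:

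- *Every standard error in this trial is 0.5–2% too small.* The range depends on an assumed N of about 50 to 200 with complete data. It applies to the group-by-time terms, not to age and sex. With fewer patients the shortfall is larger (3.4% at N = 30), and with more it is smaller (0.25% at N = 400).
- *ML accounts for all of the excess over 5%.* In step 3, REML alone removes only about half. The rest comes from treating the estimated covariance as known, which calls for a small-sample correction.
- *Drop-out makes the problem serious.* No drop-out rate is given. At an assumed 20%, the shortfall at N = 100 moves from 1.1% to 1.2%.

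**Conclusion.** The point holds as a minor one. If the reported results come from the ML fit, the group-by-time tests are slightly liberal. The size rests on the assumed N, and the rates in step 3 also on an unstructured matrix with complete data. A conclusion could change only where an ML p-value lies just below .05, within about half a percentage point at N = 50 and about a tenth at N = 200. It merits correction because the direction never varies, it touches the primary and all secondary outcomes, and nothing in the plan requires ML. It does not make the analysis invalid.

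**What to change.** Amend SAP, Main Analyses, along these lines: *Random effects and the covariance structure will be compared under REML with the fixed effects held the same. Estimates, standard errors, confidence intervals and p-values will be taken from the REML fit of the selected model, with Kenward-Roger degrees of freedom (Satterthwaite if the software lacks Kenward-Roger). Full ML will be used only for a likelihood comparison of models with different fixed effects.*

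Kenward-Roger is preferred because it adjusts the standard errors as well as the degrees of freedom, and so addresses the excess that REML alone leaves. The same rule should cover the sensitivity and per-protocol runs.

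The cost is a change to this passage and a software option. The downside is slightly larger standard errors, of the order shown above.

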### Assumptions

For each final model, the assumptions of normality, homoscedasticity and linearity will be checked by examining Q-Q plots, scatterplots of residuals versus predicted values, and scatterplots of predicted values versus observed values, respectively. In case assumptions are not met, transformations will be applied. Histograms of the residuals will be inspected for outliers. An outlier will be corrected manually if the outlier is a clear result of an error. Otherwise, the influence of an outlier will be examined by comparing results with and without the outlier. If the outlier is influential, a transformation will be applied. If not, the outlier will be retained.

### Effect Sizes

Between-group effect sizes will be calculated for each outcome at post-intervention (T2), 6-week follow-up (T3), and 3-month follow-up (T4). Cohen's  $d$  effect sizes will be obtained by performing independent T-tests in SPSS with change scores (compared to baseline) as dependent variables and group as predictor. Effect sizes of 0.2, 0.5, and 0.8 will be considered as small, medium, and large, respectively (Cohen, 1988).

#### Minimal Clinically Important Improvement

The number and percentage of participants in the intervention and control group that showed minimal clinically important improvement will be calculated for the primary outcome pain coping, defined as an increase of at least 10% on the VAS pain coping scale at T2. This number is in line with previous recommendations on minimal clinically important improvement in VAS pain (Dworkin et al., 2008). Differences in minimal clinically important improvement in pain coping between the intervention and control group will be compared with the  $\chi^2$ -test.

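### The T2 responder comparison of pain coping is an unadjusted chi-square test; adjusting for baseline would recover some power and guard against baseline-related drop-out

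*SAP*

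**What the plan says.** The SAP section on minimal clinically important improvement turns the primary outcome into a yes/no response, "defined as an increase of at least 10% on the VAS pain coping scale at T2". It then states: "Differences in minimal clinically important improvement in pain coping between the intervention and control group will be compared with the" χ²-test. It mentions no adjustment, no rule for patients without a T2 score and no explicit denominator. This is the SAP's only responder analysis.

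Two other sections bear on it:

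- **Analyses** gives the missing-data rule: "As linear mixed models are well-suited to handle missing values, missing data from drop-outs will not be imputed". The same section makes the analysis with covariates primary and the one without a sensitivity analysis.
- **Main Analyses** specifies the mixed model, in which "the fixed effects of the covariates age (centered) and sex will be included". The baseline score enters that model as an outcome, through the time dummies and without a group main effect, so the model does take account of baseline.

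**The concern.** Defining response as a rise from baseline does not remove the influence of baseline. Because of regression to the mean, patients who start low tend to rise and patients who start high tend to fall, whatever the treatment. A test that ignores baseline leaves this variation in the noise and loses power.

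The missing-data rule is the second problem. A mixed model uses the observed scores of patients who later drop out. A χ²-test on T2 response does not: without a T2 score a patient has no response status and falls out. The reason given for not imputing therefore does not carry over. If the arms lose different kinds of patients by baseline level, the remaining patients are no longer comparable on the strongest known predictor of response.

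The SAP also does not say whether its rule on covariates reaches this test, which cannot carry any. This supports the point only weakly, because age and sex alone would not remove a baseline-related bias.

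At stake is the reported responder difference on the primary outcome, not the main inference.

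**Working it through.** **Inputs.** The SAP gives the test, the 10% rule, the T2 time point and, for the mixed models, a two-sided 5% level, taken here for the χ²-test too. It gives no sample size, SD, correlation, responder rate or drop-out rate, so there is no figure to reproduce. Assumed: VAS 0–100, mean 50, SD 20, baseline–T2 correlation 0.6, response = rise of at least 10 points, 100 per arm. Scores are correlated normals clipped to 0–100. The Pearson χ²-test (no continuity correction) is compared with the Wald test for group in logistic regression on group and baseline, on the same patients.

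**Step 1: dependence on baseline.** With no effect, 48%, 27% and 12% respond for baseline below 40, 40–60 and 60 or more.

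**Step 2: complete data (10,000 trials per cell).** Monte Carlo error for power is about √(0.56 × 0.44 / 10,000) = 0.5 points. Type I error is 4.7% (χ²) and 4.8% (adjusted), so both tests are valid. Power:

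| Setting | χ² | Adjusted |
|---|---|---|
| 7-point effect, correlation 0.6, 100 per arm | 56.4% | 62.0% |
| 5-point effect | 33.1% | 36.4% |
| 10-point effect | 86.3% | 90.2% |
| Correlation 0.5 | 48.3% | 54.8% |
| Correlation 0.7 | 67.8% | 71.4% |
| 60 per arm | 37.7% | 42.1% |
| 150 per arm | 74.2% | 80.3% |

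In sample-size terms, for the first row: [(1.96 + z(0.6200)) / (1.96 + z(0.5641))]² = (2.266 / 2.121)² = 1.14, or about 14% more patients.

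**Step 3: how baseline-related loss shifts the comparison.** The three bands hold Φ(−0.5) = 30.85%, 38.29% and 30.85% of patients. Suppose the intervention arm loses 10%, 30% and 55% of them; overall loss is 0.3085 × 10 + 0.3829 × 30 + 0.3085 × 55 = 31.5%. With no effect, the responder percentage is:

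- everyone: 0.3085 × 48 + 0.3829 × 27 + 0.3085 × 12 = 28.8% (28.7% by simulation, without rounding);
- those remaining: (0.2777 × 48 + 0.2680 × 27 + 0.1388 × 12) / 0.6845 = 32.5%.

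The arm gains about 3.6 points with no treatment effect.

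**Step 4: size of the bias.** Control loses a flat 5%. Type I error is from 20,000 trials (Monte Carlo error about √(0.05 × 0.95 / 20,000) = 0.15 points). Differences are for a 7-point effect, whose true value is 14.4 percentage points (10,000 trials).

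| Intervention loss by band | Overall | Type I error, χ² | Type I error, adjusted | Raw difference | Baseline-standardised |
|---|---|---|---|---|---|
| 10/30/55% | 31.5% | 8.01% | 4.99% | 18.7 | 14.4 |
| 5/20/40% | 21.5% | 6.56% | 4.98% | 17.3 | 14.4 |
| 5/10/20% | 11.5% | 5.38% | 5.05% | 15.5 | 14.4 |

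**Step 5: other assumptions.** With 50 or 100 per arm, correlation 0.3 to 0.7, a 0.4 SD effect and either reading of 10% (1,500 trials per scenario), adjustment gains about 3 to 10 power points with complete data. There, control loses 10% and the intervention arm loses more of its low-baseline patients (30% or 45%, against 10% or 15% of the others). With no effect the raw difference then moves by about −1 to −5 points. Type I error is 5.1–9.8% for χ² and 3.9–5.9% adjusted. The sign of the bias therefore depends on who is lost.

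**Step 6: what adjustment cannot do.** If loss depends on response itself (20% against 5% lost, no effect), type I error is 8.1% (χ²) against 7.5% (adjusted) when those lost respond half as often, and 17.5% against 15.8% when they never respond.

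**Step 7: the meaning of 10%.** With no effect, 28.7% respond under 10 scale points and 39.5% under 10% of the patient's own baseline; 10.8% of patients change status. The group difference for a 7-point effect is almost the same: 14.4 or 14.5 points.

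**The case against.** The strongest reply is that this is a preference, not an error. A χ²-test on a supplementary responder table is conventional and valid with complete data or with loss unrelated to baseline. The main inference comes from a mixed model that uses baseline and all available data. The covariate rule is most naturally read as governing that model only. Nothing in the SAP suggests baseline-related, unequal loss, and the worst case above needs an extreme pattern. At 50 or 60 per arm the same pattern gives a type I error of only about 6.4–6.6%. Adjustment barely helps when loss follows response. The two readings of 10% change the reported percentages visibly and may deserve more attention than the choice of test.

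Much of this stands and sets the weight: the analysis is supportive, the covariate argument is weak, the bias is conditional and its size depends on assumed inputs. Two things remain. The SAP's stated reason for leaving drop-outs unimputed does not cover this test. And ignoring a baseline score that is already collected loses power in every complete-data setting with a true effect examined. The 10% rule does need a clarifying phrase, but it hardly moves the group difference.

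**Conclusion.** The concern holds, as a minor point. Under the assumptions above, the unadjusted test gives up about 3 to 10 power points with complete data, where it is otherwise valid. Its bias matters only when loss is large, clearly unequal and related to baseline: type I error about 8% with 31.5% against 5% lost at 100 per arm, but 5.4% with 11.5% against 5%. In the first of these patterns a true difference of 14.4 points appears as 18.7. Adjusting for baseline removes this part of the bias. It does not cure loss that depends on response itself. All sizes rest on assumed inputs, and neither the likelihood nor the direction of such loss can be judged from the SAP.

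**What to change.** In the section on minimal clinically important improvement:

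- Compare arms by logistic regression of T2 response on group, adjusted for baseline VAS pain coping, age and sex. Baseline is the term that matters; the simulations used it alone, and age and sex keep the model in line with the main analysis.
- Keep the raw number and percentage of responders per arm. Add a risk difference standardised over the baseline values of all randomised patients, with a delta-method or bootstrap interval.
- State that 10% means 10% of the scale range, if that is the intention, and that the denominator is patients with a T2 score. Report the number missing per arm.
- Say that neither the adjusted model nor imputation under missing-at-random protects against loss that depends on response. Multiple imputation, and counting missing as non-response, can be optional sensitivity analyses.

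The cost is a few sentences and one standard model on data already collected, with no extra patients. The no-imputation rule can stay. The drawback is a conditional odds ratio in place of a simple test, which the standardised risk difference offsets.

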### **Other Study Parameters**

#### Cost-effectiveness

The main research question of the cost-effectiveness analyses is to investigate the cost-effectiveness of the intervention versus standard care from a societal perspective. In order to study the potential efficiency from a societal perspective, both the medical consumption (direct costs) and productivity losses (indirect costs) will be calculated. Quality-adjusted life years (QALYs) will be computed in order to perform a cost-utility analysis. Utilities (EQ-5D) will be based on the mean values for the patients at three occasions (baseline, post-treatment and three months follow-up).

#### Implementation Eligibility

Qualitative analyses will be conducted on the interviews held with the different stakeholders regarding the evaluation of the online intervention in order to obtain information regarding the implementation possibilities of the online self-management intervention in clinical care of patients with hand OA.

### **Interim Analysis**

Not applicable.

